Inclusion Criteria

We have structured the criteria to include patients who are most likely to benefit from the intervention. This includes patients are nonadherent based on pharmacy benefit claims data and whose blood sugar is not well controlled (HbA1C ≥ 7.5). Key inclusion criteria are:

- Insurance and pharmacy coverage with Independence Blue Cross (IBC)
- 18 years or older
- Current diagnosis of Type II Diabetes Mellitus
- HbA1C ≥ 7.5 (standards defined by the American Diabetes Association) as recorded in the clinical chart at last determination
- Less than 80% medication adherence for hypoglycemic medications as determined by pharmacy benefit data in the 9 months prior to the study
- Able to communicate in English
- Willing to give informed consent

Exclusion Criteria

Participants whose medications are dispensed are excluded because the intervention focuses on the patient, not their care facility. Not agreeing to use TowerView's connected pillbox is an exclusion because it is central to our intervention. Finally, not having access to a phone is an exclusion criteria because it is the only way our group can contact the patient if needed.

- Known alcohol or illicit drug abuse
- Significant cognitive impairment at baseline as defined by a Montreal Cognitive Assessment (MoCA) exam
- Residence in a care facility that provides medication on schedule
- Unwilling to use TowerView Health's connected pillbox and accompanying medication trays
- Any active medical or psychiatric diagnosis that, based on the clinical assessment of the research team, would prevent the study participant from completing the trial such as: markedly shortened life expectancy (e.g. diagnosis of metastatic cancer, end stage renal disease on dialysis, New York Heart Association (NYHA) Class III or IV heart failure, active psychosis or suicidal ideation, etc.) or dexterity/motor impairments (e.g. severe arthritis, neuromuscular disorders, etc)
- Lack a mobile or landline phone

Subject Recruitment and Screening

We will recruit 150 patients identified through the Pennsylvania Integrated Clinical and Administrative Research Database system and Independence Blue Cross/Catamaran databases. Patients with Type II DM, an HbA1C \geq 7.5, and IBC medical and pharmacy coverage will be identified.

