Patients will be consented by a trained research coordinator and have the following information collected from them:

- Electronic mailing address and phone number
- Blood pressure-once at the beginning and once at the end of the visit
- Demographic survey
- Montreal Cognitive Assessment (MoCA exam)- a screen for cognitive impairment
- Cumulative Illness Rating Scale (CIRS)- a measure of comorbid illness burden
- Short Form 12 (SF-12)- a measure of general quality of life
- Brief Medication Question (BMQ)- a self reported assessment of medication adherence and medication adherence related factors (e.g. cost burden of drugs)

Concluding Visit

Patients will return their connected pillbox and have the following information collected from them:

- Blood pressure- once at the beginning and once at the end of the visit
- HbA1c test and lipid panel if data cannot be abstracted from the chart
- Patient satisfaction and attitudes toward adherence system

The care coordinator will also assist the patient in transitioning from the tray to another method of receiving their medications. Patients will have the option of either remaining with Friendship Pharmacy or be transferred back to their original pharmacy.

Methods

Measuring Adherence

Proportion of Days Covered (PDC) is the metric currently used by CMS and NCQA to assess patient medication adherence; the metric is calculated using pharmacy benefit data. The present study utilizes an interval-based PDC calculation defined as medication possession during the interval from the index date (the patient's study start date) to the end of the period being assessed (the patient's end date). In this way, the number of days of medication supplied throughout the period becomes the numerator and is divided by the number of days in the overall period itself. Intervals during which patients are hospitalized or in hospice are excluded from the PDC calculation

As PDC is an assessment of medication adherence for a single drug the calculation must be modified for patients taking multiple medications. Of interest in this study is patient adherence to oral hypoglycemic drugs. Our group recognizes the following categories as oral hypoglycemic agents: sulfonylurea, metformin hydrochloride, glitazones, acarbose, and meglitinides.

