For patients taking multiple hypoglycemic agents the PDC for each drug is calculated then averaged to arrive at a mean group PDC. Mean group PDC will be used as a patient inclusion criteria as well as in the post study analysis for patients taking multiple hypoglycemic agents. Pre-study adherence rates will be determined using a 9-month estimate of PDC for the hypoglycemic drugs in a patient's medication schedule.

Measuring Persistence

Medication persistence relates to the length of time a patient remains on a medication without discontinuation. Patients are deemed to have discontinued therapy when more than 30 days have elapsed without a prescription refill. The persistence length will be calculated from the study start date to the expected end date of the last prescription prior to the patient discontinuing therapy.

Post Study Analysis

The primary outcome of interest in the present study is improvement in adherence; however, our group also plans to analyze the following secondary variables if the sample size allows:

- Medication Persistence
- Blood glucose (A1C)
- Blood pressure control
- Body mass index,
- ER visits
- Absolute costs,
- Overall healthcare utilization,
- Patient satisfaction with service,
- Time to first research coordinator outreach
- Number of research coordinator outreach events
- Text message and phone call trends

We also plan to perform regressions that explore how the following factors influence study outcomes:

- Age and Gender
- Insurance Line of Business (e.g. HMO, PPO, POS, MA HMO, MA PPO, etc)
- Pre-study medication adherence
- Pharmacy preference
- Type and number of comorbidities
- Patient drop-out from the study

Risks

Patients in the treatment group face potential confusion over use of new of device and mode of receiving their medication. This risk will be mitigated through patient education. Each patient will be trained on how to use the device as well as sent home with a detailed document highlighting how to use their smart pillbox and how to navigate the TowerView Health platform. Patients will also be given a number they can call at anytime to receive detailed assistance if challenges arise.

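### PDC drops only hospital and hospice days, so temporary nursing-facility or rehabilitation stays are scored as the patient's own adherence in the screen, the baseline and the primary endpoint

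*Combined protocol and SAP*

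**What the plan says.** Measuring Adherence defines PDC from claims ("the metric is calculated using pharmacy benefit data"). In the calculation, "the number of days of medication supplied throughout the period becomes the numerator and is divided by the number of days in the overall period". The only days taken out are those in the sentence "Intervals during which patients are hospitalized or in hospice are excluded from the PDC calculation". Neither term is defined further.

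The same measure is used three times. It is the entry screen (Inclusion Criteria: "Less than 80% medication adherence for hypoglycemic medications as determined by pharmacy benefit data in the 9 months prior to the study"). It is the baseline (Measuring Adherence: "Pre-study adherence rates will be determined using a 9-month estimate of PDC for the hypoglycemic drugs in a patient's medication schedule"). It is also the follow-up value in the change score that the Statistical Analysis section compares between arms.

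The Exclusion Criteria explain why care facilities matter: "Participants whose medications are dispensed are excluded because the intervention focuses on the patient, not their care facility". The criterion that follows is "Residence in a care facility that provides medication on schedule".

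Measuring Persistence has its own rule, with no institutional exclusion of any kind: "Patients are deemed to have discontinued therapy when more than 30 days have elapsed without a prescription refill".

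**The concern.** The plan accepts that when a facility gives the drugs, adherence is the facility's and not the patient's. It applies this to people living in such a facility at entry, but not to days. A nursing or rehabilitation stay that ended during the look-back, or one that begins after randomisation, is not residence at entry and is not clearly a hospital or hospice interval. A patient discharged from hospital to a nursing facility has the first interval removed and the second scored, although staff give the drugs in both.

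Two things are at stake. In the look-back, an adherent patient may be enrolled as nonadherent and then appear to improve in either arm. In follow-up, the patient's PDC reflects days on which trays, pillbox and reminders cannot act. Both add noise to the primary change score and dilute a real effect. Recruitment includes geriatric clinics, and the planned regressions list Medicare Advantage plans, so such stays are foreseeable.

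**Working it through.** **Plan's own figure.** Inputs from Target Population and Statistical Analysis: difference 15 points, SD 30, two-sided alpha 0.05, power 80%, dropout 15%.
n per arm = 2 × (1.960 + 0.842)² × 30² / 15² = 62.8, so 63. Then 63 / 0.85 = 74.1, so 75. The stated 75 per arm reproduces. With 75 × 0.85 = 63.75 completers per arm, power is 0.806 (normal approximation).

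**Notation.** a = true PDC outside the stay, L = facility days, D = days in the window. I take D = 274 for 9 months and 183 for 6 months. The documents give neither a frequency nor a length of stays, so L and the proportion affected, f, are assumptions.
- No claims for the stay: observed PDC = a(D − L)/D, a loss of aL/D.
- Stay fully covered by claims: observed PDC = [a(D − L) + L]/D, a gain of (1 − a)L/D.

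**Entry screen, worst case (no claims).** Observed PDC falls below 0.80 when L > 274 × (1 − 0.80/a):
- a = 0.85: 16.1 days
- a = 0.90: 30.4 days
- a = 1.00: 54.8 days

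For example, 60 days at a = 0.95 gives 0.95 × 214/274 = 74.2%. The patient enters as nonadherent and, if unchanged at 95%, shows a gain of about 21 points with no intervention effect.

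**Follow-up, one patient.** Take a = 0.65, within the 57.6-67.9% range of usual-care means tabulated under Hypothesis, and L = 60:
- No claims: loss = 0.65 × 60/183 = 21.3 points, or 21.3/75 = 0.28 points on an arm mean.
- Fully covered: gain = 0.35 × 60/183 = 11.5 points.

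**Trial level, stays balanced, no claims.** The loss common to both arms cancels. What remains is that the effect cannot accrue on facility days: effect = 15 × (1 − fL/183).
- f = 2%, L = 20: 14.97, power 0.804
- f = 5%, L = 60: 14.75, power 0.793
- f = 10%, L = 60: 14.51, power 0.779

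These hold the SD at 30. Letting the stays add variance, SD = √[900 + f(1 − f)(65L/183)²]. This gives 30.02, 30.36 and 30.67 in the three cases, and power 0.804, 0.783 and 0.761.

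**The case against.** The strongest reply is that the problem is rare, partly handled and mostly cancels. Much of that stands. Long-term residents are excluded at entry, as are several groups plausibly prone to facility stays: significant cognitive impairment, dialysis, advanced heart failure, severe motor impairment. The undefined term for hospital stays might already cover inpatient rehabilitation, though not nursing-facility days. Randomisation balances stays in expectation. A chance split of four 60-day stays to none would move the difference by 4 × 0.28 = 1.1 points, against a standard error of 30 × √(2/75) = 4.9, and the t test already allows for chance imbalance.

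A reader might infer that every facility day is scored as uncovered. The text does not say so. The numerator counts days supplied, so a fill already dispensed counts wherever the patient is. The loss arises when later refills are delayed, which makes the thresholds above worst cases, and it reverses if the facility bills the benefit. A reader might also infer that a patient wrongly screened in has no room to benefit. True PDC of 85% or 90% still leaves 15 or 10 points.

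Imbalance could be systematic, since only the treatment arm gets repeated refill reminders, and a patient prompted to refill during a stay would be scored as covered. The documents neither establish nor rule this out. As an extreme, 60-day stays in 10% of one arm alone would move the difference by 0.10 × 21.3 = 2.1 points.

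Finally, removing post-randomisation days conditions the endpoint on an event that treatment might affect, and keeping them is defensible under intention to treat. But the plan already removes hospital days, so the extension introduces no new kind of trade-off. It is a reason for a sensitivity analysis.

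**Conclusion.** The gap is real on the text: the stated rule mis-scores patients with temporary facility stays, against the plan's own reason for excluding facility residents. It affects the screen, the baseline and the primary endpoint. Because the PDC interval is described as running from the study start date, it is not even explicit that the hospital and hospice rule applies to the 9-month look-back.

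The effect is material for an affected patient, in either direction, and small for the comparison: under the balanced assumptions shown, an effect of about 14.97-14.51 and power of about 0.80-0.78 with the SD held at 30 (0.76 in the most extreme case if the SD is allowed to grow). A reader might infer that the arm-mean losses bias the treatment comparison or that the sample size is wrong. Neither is supported: common losses cancel, and the 75 per arm reproduces. The trial-level figures rest wholly on assumed frequency and length of stay. The persistence gap is of the same kind but concerns an exploratory endpoint. Low-to-moderate priority.

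**What to change.** Amend the exclusion sentence under Measuring Adherence so that hospital, hospice and any skilled-nursing, rehabilitation or other facility stay in which medication is administered is removed from both numerator and denominator. Say that stays are identified from the insurer's medical claims. Apply the rule identically to the look-back (screen and baseline) and to follow-up, in both arms. Under Measuring Persistence, do not count these days, or hospital days, towards the 30-day gap. Report PDC without the added exclusion as a sensitivity analysis. Settle the wording before outcome data are seen by arm.

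The cost is a sentence in each of the two sections and one extra analysis. The documents do not name a source for identifying stays, but participants have the insurer's medical coverage, its informatics department performs the analysis, and the emergency-visit, cost and utilization endpoints imply use of medical claims. The downsides are a slightly shorter denominator for a few patients, and that stays not billed to the insurer remain unseen. The sample size need not change.

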
1. The pre-filled medication trays are provided by a pharmacist, which overcomes medication access issues as well as the inconvenience of manually organizing medications.
2. The electronic pillbox, which monitors adherence that triggers text message or phone reminders in instances where patients forget or ignore medication doses
3. Research coordinator alerts, which trigger outreach events that employ a motivational interview in order to improve patient adherence

A study involving multiple interventions is rooted in literature findings that medication nonadherence has multiple drivers, ranging from forgetfulness and confusion over treatment rationale to logistical difficulties in getting medication refills and drug costs. While our group is unable to address the key cost considerations patients face in remaining adherent, our multi-modal approach improves ease of use and provides reminders that may improve medication adherence.

Future studies may look to add additional research arms in order to isolate the benefits from the various elements of the currently proposed intervention. Such studies may also include larger sample sizes in order to be powered to discern differences between the treatment and control groups for clinical markers such as A1C or blood pressure control.

Hypothesis

Combined use of a technology enabled pill box, targeted text or phone reminders, pre-filled medication trays, and research coordinator outreach will result in a 15% improvement in medication adherence when compared to a usual care control group.

The range of adherence improvements observed in the literature under various adherence interventions varies from 5% improvement to over 40% improvement, however, a number of intervention approaches cluster between a 10-20% improvement (see table below). As a result, our group has conservatively estimated an expected improvement in medication adherence of 15% between the research treatments and usual care arms of the present study. Usual care is defined as the existing clinical practice guidelines used by physicians at the University of Pennsylvania for managing patients with diabetes and additional comorbidities.

Authors	Intervention	Usual Care PDC (SD)	Intervention PDC (SD)	Study Population
Lee et al 2006	Pharmacist education, multidose blister packaging	61.2% (13.5%)	97% (5%)	Geriatrics
Murray et al 2007	Pharmacist Intervention	67.9%	78.8%	Heart Failure
Morgado et al 2011	Pharmacist Intervention	57.6%	74.5%	Hypertension

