We propose a randomized control clinical trial. Random number generation will be used to randomize patients to either the treatment group (connected pillbox) or control group (usual care). The patient will only be randomized after he or she has been briefed on the intervention and consented to participating. In this way both patients in the treatment and control groups will receive the same education regarding adherence so as to not bias the study. Patients in both the research treatment and control group will be compensated equally for their participation in the study.

Study Intervention

The study intervention is multi-modal and consists of 1) prefilled medication trays that are shipped to patient's home 2) a connected pillbox that senses when doses are missed and can initiate phone call or text reminders and 3) research coordinator outreach triggered by nonadherence. A detailed overview of each component of the intervention is presented below:

Prefilled Medication Trays

The study sponsor, TowerView Health, has developed plastic trays designed to hold all the medications in a patient's regime. Each tray has 21 medication compartments- 3 compartments (morning, afternoon, nightly meds) for each day of the week. Patients in the research intervention will receive monthly shipments of 5 prefilled medication trays from Friendship Pharmacy, Inc., an IBC participating long-term care and retail pharmacy, located at [name].

After consenting to participate in the study, the patient or patient's caregiver will provide the research coordinator with a complete list of pharmacies used by the patient. This information will be shared with the Friendship Pharmacy pharmacist who will initiate the transfer of all scripts from patient's existing pharmacy to Friendship Pharmacy. A nurse practitioner or physician at Penn Medicine will initiate any scripts that need to be rewritten. In instances where prior authorization is required or a script is denied at adjudication the Friendship pharmacist will reach out to the physician or nurse practitioner to receive authorization or make an appropriate medication change.

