Patients in both the treatment and control arms will receive an identical overview regarding the proposed intervention and randomization will only occur after the consent process has been completed. Patients in the control arm will receive usual care and can continue using their existing pharmacy. Patients in the treatment group will begin receiving their medications in pre-filled medication trays from Friendship Pharmacy. Patients will receive 5 trays on a monthly basis in order to accommodate a 30-day, insurance-reimbursed fill schedule.

As much as possible our group will attempt to collect data as part of usual clinical practice. For example, we will attempt to consent patients with upcoming clinic visits who meet enrollment criteria on the same day as their existing appointment. For patients whose appointment schedule does not permit us to do so we'll look to schedule a research visit on a day and time that is most convenient.

We will also attempt to utilize existing laboratory tests so as to not duplicate services. Given the present study assesses patient adherence for hypoglycemic medications, we would like to have an HbA1c measure for each patient at the onset and conclusion of the study. Rather than simply re-order this test we have set a 45 day window such that if an A1C was ordered as part of usual care in the 45 days before the patient's study start date or end date we will abstract that value from the patients chart for use in our analysis.

As clinical guidelines recommend that patients with poorly controlled glycaemia have an A1C taken quarterly, we reserve the right to request an A1C for patients who have not had one as part of usual care. If none of the conditions previously described are met we will order an A1C under the research protocol, thereby incurring a research expense on behalf of the patient.

LDL, HDL triglycerides, and total cholesterol levels are also of interest to our group in instances where the patient has both diabetes and hyperlipidemia. As a lipid panel is typically ordered once a year for patients with hyperlipidemia our group has set a 3 month window from the study start and end date. If the patient's lipid panel was drawn as part of usual care during this 3-month time window we will abstract the value from the patient's chart. Below is a summary of the information we will collect at the two visits common to all patients participating in the study.

Induction Visit

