¹ Under Pennsylvania law, patients who have diabetes are eligible to receive a blood glucose monitor and strips free of charge under their insurance benefit. Patients who have not yet utilized this IBC benefit will be assisted by the research coordinator to do so as part of the study.

costly interventions involving case or disease management programs. There is also a chance there is no benefit associated with the study intervention.

Subject Confidentiality

All aspects of this study are conducted in HIPAA compliant environment. The TowerView Health software is hosted on a dedicated, HIPPA compliant server using Amazon Web Services (AWS). Use of encrypted computer files, de-identified documents, and storage of all patient questionnaires in locked offices/cabinets will reduce the risk of loss of confidentiality. No verbal or written information concerning study participants will be released without their express written consent, unless required under federal law. All data analyses will be performed using participants' identification numbers rather than names so as to minimize the number of study team members who know the identity of the research participants.

Compensation

Participants can receive up to \$100 for participating in this study. Checks will be distributed in two stages \$20 at the 3 month study mark, and \$80 at the 6 month study mark. If participants withdraw from the study before the next milestone they will be able to keep the monies for their existing enrollment but will not be able to receive compensation for upcoming milestones.

In addition to compensation for participating in the study there are also out of pocket costs for medications. These costs may change for certain patients given that they are being transferred to Friendship Pharmacy from their existing pharmacy. Wherever possible we will work closely with IBC/Catamaran to ensure cost parity between patient's previous pharmacy choice and Friendship Pharmacy. In instances where this is not possible TowerView Health will make up the difference by compensating patients for their increased cost sharing. We acknowledge that for some medications the difference in cost between Friendship and existing pharmacy may be too high for our group to make up the difference. In these cases we will have to disenroll patients from the study unless they agree to accept the higher out of pocket costs associated with the study.

Risk/Benefit Assessment

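### Disenrolment over pharmacy cost can occur only in the treatment arm, and the plan does not say how these patients are analysed, so the primary comparison is exposed to bias of unknown size and direction

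*Combined protocol and SAP*

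**What the plan says.** **The rule.** The Compensation section accepts that out-of-pocket costs may shift: "These costs may change for certain patients given that they are being transferred to Friendship Pharmacy from their existing pharmacy". It then sets out a sequence. The team seeks cost parity through IBC and Catamaran. Failing that, the sponsor reimburses the difference. Where the gap is too large to reimburse, "In these cases we will have to disenroll patients from the study unless they agree to accept the higher out of pocket costs".

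**Who is transferred.** Under Post Enrollment Events, "Patients in the treatment group will begin receiving their medications in pre-filled medication trays from Friendship Pharmacy", whereas "Patients in the control arm will receive usual care and can continue using their existing pharmacy".

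**When.** Study Design states: "The patient will only be randomized after he or she has been briefed on the intervention and consented to participating". Post Enrollment Events repeats that "randomization will only occur after the consent process has been completed". On the transfer itself, Prefilled Medication Trays says: "After consenting to participate in the study, the patient or patient's caregiver will provide the research coordinator with a complete list of pharmacies"; the list goes to the study pharmacist, who starts moving the prescriptions. No section dates the cost check.

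**Link to the outcome.** The first Study Intervention section counts "logistical difficulties in getting medication refills and drug costs" among the drivers of nonadherence.

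**Analysis.** Statistical Analysis specifies intention to treat for the primary endpoint, the change in PDC compared by an unpaired t test. Patients who do not complete, through death or withdrawal, have their last available adherence level carried forward. Early Withdrawal of Subjects gives three grounds for removal without consent (safety or health, instructions not followed, study stopped) and the participant's own right to leave. Cost is not mentioned there, nor in the inclusion and exclusion lists. Measuring Adherence says PDC is calculated from pharmacy benefit data.

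**The concern.** The cost condition works like an eligibility criterion that only one arm can fail. A control patient with the same drugs and the same plan keeps the old pharmacy and stays in the trial, while the matching treatment patient may be removed. If the removed patients differ in how their adherence would have changed, the arms are no longer comparable as randomised.

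The intention-to-treat statement does not settle this. If the patients are left out of the analysis, it is not followed. If they are kept by carry-forward, the value carried is either the 9-month pre-study PDC, which gives a change of zero, or a PDC over a few days or weeks, which a single 30-day fill can push towards 0% or 100%. Neither is the 6-month result of being assigned to the intervention. Any harm to adherence that the pharmacy switch causes through cost would also go unmeasured in these patients.

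**Working it through.** **1. One arm only.** Compensation ties the cost change to transfer, and Post Enrollment Events transfers only the treatment group. The rule cannot reach a control patient.

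**2. After randomisation.** This is inferred. Randomisation follows consent, only patients allocated to treatment have a reason to be transferred, disenrolment presupposes enrolment, and no price check before allocation is described.

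**3. The plan's own sample size.** Inputs from Target Population and Statistical Analysis: difference 15 points, SD 30, two-sided 0.05, power 80%, dropout 15%.
- Per arm: 2 × (1.96 + 0.84)² × 30² / 15² = 62.8, so 63.
- With dropout: 63 / 0.85 = 74.1, so 75.
- Power with 75 × 0.85 = 63.75 completers per arm: 0.806.

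The stated 75 per arm is reproduced, and no design figure is in dispute.

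**4. Effect of each way of handling these patients.** The documents give no rate and no outcomes, so the following inputs are assumptions:
- f: share of the treatment arm disenrolled for cost.
- g: points by which these patients' usual-care change in PDC is worse than that of the others.
- c: their mean usual-care change.
- The effect is 15 points on the intervention and 0 once disenrolled.

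Formulas:
- All followed to month 6: effect of assignment = 15(1 − f), with no selection bias.
- Excluded: estimate = 15 + f·g, so bias = f(15 + g).
- Pre-study PDC carried forward: their change is set to 0 instead of c, so bias = −f·c.

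| f | All followed | Excluded, g = 0 to 20 | Bias if excluded | Carry-forward bias, c = +10 / −10 |
|---|---|---|---|---|
| 5% | 14.25 | 15.0 to 16.0 | +0.75 to +1.75 | −0.5 / +0.5 |
| 10% | 13.5 | 15.0 to 17.0 | +1.5 to +3.5 | −1.0 / +1.0 |
| 20% | 12.0 | 15.0 to 19.0 | +3.0 to +7.0 | −2.0 / +2.0 |

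With no true effect, the bias from exclusion is f·g. At g = 20 this is 1.0, 2.0 and 4.0 points, and the two-sided type I error (no other losses) becomes 0.055, 0.068 and 0.120. At g = 0 it stays at 0.050.

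**5. Power.** If cost disenrolment came on top of the planned 15% dropout, in the treatment arm only, power at 15 points would be 0.794, 0.780 and 0.748 for f = 5%, 10% and 20%.

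**The case against.** The strongest reply is that disenrolment describes participation, and no section removes these patients from the analysis set. Intention to treat is promised, carry-forward is specified, and the outcome comes from claims, which can exist without trays or visits.

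Mitigation is also real. Parity efforts, sponsor payment and the patient's option to accept the cost all come before disenrolment. The study pharmacy participates in the insurer's network, and the introduction describes most of the oral drugs as low-cost generics. Patients are briefed before randomisation, and those unwilling to use the trays are excluded from both arms. Finally, a large price gap between two pharmacies is not the same as being cost-burdened at one's own, so a worse prognosis is a hypothesis.

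Much of this stands. The number affected may be small, the timing is inferred, and the link with outcome is plausible but not shown. What does not stand is that the analysis text resolves the matter. It names only death and withdrawal, and a removal by the study team over cost is classified nowhere. If it does count as withdrawal, carry-forward supplies the wrong quantity for an early leaver. That claims could provide the 6-month outcome is a reason to specify their use; the plan does not say they will be used after disenrolment.

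**Conclusion.** The point holds as a risk of bias. The plan contains a loss that only the treatment arm can suffer, very probably after randomisation and plausibly related to adherence, and neither available reading of the analysis text deals with it properly. Size and direction cannot be determined from the documents. Exclusion favours the intervention if these patients would have done worse than the rest of the treatment arm. Carrying a pre-study value forward works against the intervention if they would have improved under usual care, and for it if they would have declined.

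A reader might infer that the result is biased towards the intervention by about 1 to 4 points. That range comes from assuming 4 to 11 of 75 patients removed, each 20 to 30 points below the rest of the arm: 4/75 × 20 = 1.07 and 11/75 × 30 = 4.4. The documents do not support it as a finding. Neither input is in the protocol, and deletion is not stated. The deficit would also have to lie in the change score, since any part already present at baseline cancels.

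The correction is worth making before enrolment, because the plan makes no provision for recovering the missing outcomes afterwards.

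**What to change.** Reconcile Compensation, Early Withdrawal of Subjects and Statistical Analysis so that they say the same thing:

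- A patient who meets the cost problem after randomisation stays in the study for follow-up. What happens to that patient's medication supply is for the investigators and is not part of this point.
- PDC is taken from IBC claims to month 6 and replaces carry-forward for these patients.
- They are analysed in the arm to which they were allocated.
- Cost disenrolments are reported by arm, with numbers and timing.

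Optionally, remove most of the problem at source. Patients are asked to bring their medications to the consent visit and, after consent, to list their pharmacies. Price that list before allocation and apply the cost condition to every patient as an eligibility criterion.

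**Cost.** The main change is wording plus some extra claims extraction. The estimate may be slightly diluted, because it then includes patients who did not receive the intervention. On the assumptions above, with all 75 per arm followed and no other dilution, power is 0.829, 0.787 and 0.688 at f = 5%, 10% and 20%, against 0.865 with no disenrolment. The optional step needs a price check for all consented patients, including future controls whose medication lists would have to be shared for pricing, and may put a short delay between consent and randomisation.
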